Veterans with SCI are often immunosuppressed and have chronic health conditions (e.g. cardiovascular disease, respiratory compromise, metabolic disease including diabetes mellitus) that place them at a potentially higher risk of complications and more severe symptoms should they contract COVID-19. Additionally, individuals with SCI may be debilitated from poor nutrition, experience chronic pressure injuries with or without osteomyelitis, have concurrent respiratory infections, and experience frequent urinary tract infections (UTI). Of note, individuals with higher cord lesions who have difficulty clearing secretions from their lungs because of an impaired or absent cough due to respiratory muscle weakness from paralysis are at a higher risk of developing pneumonia and its complications. The signs and symptoms of COVID-19 may be different in individuals with SCI than the general population. For example, the high fevers characteristic of COVID-19 in the general population may not be observed in persons with tetraplegia, who experience lower core body temperatures, thereby requiring a different definition of fever for symptom surveillance and clinical diagnosis. Also, the common feeling reported of chest pressure may be absent in those who are insensate in this area. Persons with respiratory compromise, may experience shortness of breath earlier in the course and decline more rapidly, an indication for earlier admission and closer surveillance.

In the Veterans Health Administration (VHA) and the Spinal Cord Injury and Disease (SCI/D) National Registry, there are 17,806 Veterans with SCI. It is not known how many Veterans with SCI are, or will be, directly infected by this virus, nor the severity of their symptoms and survival rates. However, it is anticipated that, due to their high risk of immunodeficiency and other comorbidities, the occurrence may be higher, with the potential for more severe symptoms and greater mortality than in the general population.

Additionally, of great concern, is the anecdotal report of loss of services, including routine medical care for non-COVID-related conditions (i.e. pressure injuries, urinary tract infections, etc.), loss or interruption of caregiver services, and wheelchair or assistive devices repair options, that has been an unfortunate consequence of the pandemic. [name], President and CEO of United Spinal Association, Inc. (a membership of 58,000 nationwide which includes about 1500

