A follow-up “in-person” visit to update information from the initial survey and to collect blood samples for virus testing, anti-viral antibody, and other immune analyses relevant to the COVID-19 disease will be planned at least one month after the initial survey. The antibody, cytokine, and other immunological analyses at a future date when our country has recovered from this current pandemic will be critical for determining the number of Veterans with SCI who were infected with the virus, the relationship with the signs and symptoms of infection, if any, and the rate of survival in this population sample. There will also be an option to complete the follow-up survey over the phone for participants who do not wish to travel to the local VAs. An option to complete the blood draw in the home will be available through the services of a VA contracted phlebotomist vendor, ExamOne.

The initial survey and follow-up survey, medical chart review, and blood draw are intended to capture the following information:

Questions related to the **direct impact of COVID-19** on Veterans with SCI will be collected by phone interview using Doximity. Doximity allows for a registered physician (or delegate) to log in and set a phone number, such as each local VA Medical Center who would be represented in this study. The person receiving the call sees the VA Medical Center as the caller ID. Participants will also have the option to complete the initial survey by in-person interview.

In Veterans with SCI, the following information will be collected (but not limited to):

- a) The number who are/were diagnosed with COVID-19, determined from the medical records and/or interviews;
- b) The number who presented with symptoms, determined from the medical records and/or interviews;
- c) The type, duration and severity of symptoms, determined from the medical records and/or interviews;
- d) The number who have anti-SARS-CoV-2 antibodies, with testing to be performed at least one month after initial interview (or whenever is deemed safe for an in-person visit to the medical centers); and
- e) The number and characteristics of those who survived.

Questions related to the **indirect impact of COVID-19** pandemic on Veterans with SCI who rely on caregiver assistance and other services that may have been interrupted during the COVID-19 outbreak will be determined via interview.

The following information will be collected (but not limited to):

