There will be an option to complete the blood draw at the participant's home through services provided by a VA contracted phlebotomist vendor. The vendor, ExamOne, will only provide the blood collection service. They will not be engaged in research activities. All questions about the study (other than blood collection visit schedules and blood draw procedures) will be directed to the local site team and/or the Chair's Office. ExamOne will spin down the samples, as appropriate, and deliver them to the local site personnel for freezing or local site lab analysis.

All blood samples will be labeled with the study ID, date and a coded participant ID number. The serum and plasma of each spun down tube and the PAX gene tube with whole blood will be stored in a freezer for shipment to the James J Peters VA Medical Center, Bronx, NY (Chair’s Office). The cytokine testing will include: Interleukin-1 (normal range 0-5 pg/ml); Interleukin-6 (normal range 5-15 pg/ml); Interferon-alpha (normal range 0 to 35 U/L), Interferon-gamma (normal range <8.1 pg/mL), tumor necrosis factor (TNF)-alpha (normal range ≤ 2.8 pg/mL, and TNF-gamma (normal range <10 pg/ml).

The optimum methodology to perform the antibody analyses will be determined in consultation with the VHA Infectious Disease Service and the Clinical Laboratory at the time of sample analysis. In the future, biological values and other clinical data will may be compared to other populations, including Veterans without SCI or non-Veterans with SCI.

Timeline: It is estimated the study staff can complete the initial surveys on screened participants by the end of September 2021. Once the medical centers have re-opened to outpatient visits, the in-person or phone visits for the follow-up surveys and in-person visits for blood draws can be completed by the end of FY21, which is within the timeframe of the completion of CS #2003. An estimated timeline is provided (Table 22).

Table 22. Timeline	FY20 Q3	FY20 Q4			FY21 Q1 to Q4			
	Jun-20	Jul-20	Aug-20	Sep-20	Q1	Q2	Q3	Q4
Administrative approvals ¹	✓							
CIRB submission		✓						
CIRB approval					✓			
Survey development & refinement	✓	✓						
iDatafax form for the survey			✓	✓	✓			
Train CS #2003 staff (via Teams or other)					✓			
Initial surveys and chart review						✓	✓	✓
Follow-up surveys, chart reviews & blood draws							✓	✓
¹ CS#2003 Executive committee and CSP VACO review and approvals								

D. Relevance

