This information will be used to inform the VHA of the medical, sociological and/or quality of life impacts from the COVID-19 pandemic on Veterans with SCI who were screened for CS #2003. Specifically, for the medical impact, we will learn about the number in this sample who were

infected, their symptoms (if any) and severity, any associated illnesses, immunological responses, and the number of individuals who recovered and survived. The sociological and quality of life impact of this virus will also be reported, including the interruption of vital services such as caregivers, medical appointments, wheelchair repair, levels of anxiety, and other aspects. We will also learn about any positive occurrences that may be reported such as usage of telemedicine, and more access to online social groups or web-based activities. **Important benefits from this project will be to improve preparedness for future local and/or national disasters in order to protect Veterans living with SCI from untoward exposure and/or loss of services.**

Notes for consideration:

- On the follow-up visit, if the participant has a positive test for anti-SARS-CoV-2 antibodies, we will know that they had the COVID-19 infection at some time in the past (and even could have been asymptomatic); these individuals would be categorized as persons who have survived. If they test negative for anti-SARS-CoV-2 antibodies, then we will know they had not been infected as of the date of the test.
- Some of the Veterans with SCI who participate in the baseline/initial survey will have already been diagnosed with viral infection and/or COVID-19 (many of our institutions already have some Veterans with SCI who have tested positive for the virus). Some Veterans with SCI are being treated for COVID-19 based on severe symptoms and may not have been tested for viral infection by lab diagnostics until after they have been treated. Other individuals with less severe symptoms, that did not require hospitalization, may not have been tested for COVID-19 using lab tests. In these cases, the antibody testing will reveal how many people with SCI in our study sample had the virus.

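### The COVID-19 sub-study reads antibody results as certain proof of past infection or of none, with no allowance for assay error and no rule for a negative test in a diagnosed case

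*Combined protocol and SAP*

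**What the plan says.** Section XX.D (Relevance, notes for consideration) gives the reading of each antibody result. After a positive test, "we will know that they had the COVID-19 infection at some time in the past", and the person is categorised as a survivor. After a negative test, "then we will know they had not been infected as of the date of the test". For participants who were ill but not lab-tested at the time, it adds that "the antibody testing will reveal how many people with SCI in our study sample had the virus".

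Other parts of Section XX bear on this:

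- XX.B calls the antibody, cytokine and other immunological analyses "critical for determining the number of Veterans with SCI who were infected with the virus", and also for the relation to symptoms and for survival.
- XX.B says "Veterans with SCI are often immunosuppressed".
- XX.B lists the direct-impact data. Diagnoses and symptoms come from medical records and/or interviews, and a separate item counts those who have antibodies. The draw is set at least one month after the initial interview; it is not timed to infection.
- XX.C leaves the assay open until the samples are analysed, with laboratory staff also to be consulted: "The optimum methodology to perform the antibody analyses will be determined in consultation with the VHA Infectious Disease Service". No sensitivity or specificity is given.
- XX.B mentions virus testing of the follow-up blood sample, but the itemised tube list in XX.C contains no virus test.
- XX.E (Limitations) covers selection and access to visits, not test error. Section XIII (the SAP) does not cover the sub-study.

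**The concern.** The two statements amount to a classification rule with sensitivity and specificity both equal to 1. Nothing in the documents supports that, and two of their own statements argue against presuming it: the assay is unchosen, and the sample is described as often immunosuppressed.

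The rule also collides with the other data the sub-study collects. XX.D itself expects some participants to have been diagnosed already, and XX.B records those diagnoses. If such a person tests negative, the two sources disagree, and the only stated reading of a negative result is that the person was never infected.

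At stake are the number of past infections among people never tested or diagnosed (the group for whom XX.D relies on antibodies), the share of infections without symptoms, and the denominator of any survival rate. A false positive in someone without symptoms would be counted as an asymptomatic infection and as a survivor.

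**Working it through.** **Sample size, from the plan.** The 15 site counts in Table 21 sum to 423. XX.C expects 80% or 90% to take part: 423 × 0.80 = 338.4 (stated 338) and 423 × 0.90 = 380.7 (stated 381). Both reproduce. I use N = 338 and assume that all are tested. The blood draw is optional, so the number tested may be lower.

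**Assumed inputs.** The documents give no prevalence (p), sensitivity (Se) or specificity (Sp). All three are assumptions.

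**Formulas.**

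- Missed infections: FN = N × p × (1 − Se)
- False positives: FP = N × (1 − p) × (1 − Sp)
- Net error in the count: FP − FN
- Share of positives that are false: FP / (N × p × Se + FP)

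| p | Se / Sp | Truly infected | Missed | False positive | Net error | Positives that are false |
|---|---|---|---|---|---|---|
| 10% | 0.80 / 0.98 | 33.8 | 6.8 | 6.1 | −0.7 | 18% |
| 10% | 0.95 / 0.995 | 33.8 | 1.7 | 1.5 | −0.2 | 5% |
| 5% | 0.80 / 0.98 | 16.9 | 3.4 | 6.4 | +3.0 | 32% |

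First row in full: FN = 338 × 0.10 × 0.20 = 6.8; FP = 338 × 0.90 × 0.02 = 6.1; false share = 6.1 / (27.0 + 6.1) = 18%.

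**How far the net error can move.** These rows pair a weaker Se with a weaker Sp. Crossing the same ranges widens the result:

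- p = 10%, Se 0.80, Sp 0.995: 1.5 − 6.8 = −5.2 (unrounded 1.52 − 6.76).
- p = 5%, Se 0.95, Sp 0.98: 6.4 − 0.8 = +5.6 (unrounded 6.42 − 0.85).

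Over a wider assumed grid (p 2–30%, Se 0.70–0.95, Sp 0.95–0.995) the net error runs from about −29 to +16. It is zero when p = (1 − Sp) / [(1 − Sp) + (1 − Se)], for example 0.01 / 0.11 = 9.1% at Se 0.90 and Sp 0.99.

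**Check of the correction.** The Rogan-Gladen estimate is (apparent prevalence + Sp − 1) / (Se + Sp − 1). In the first row the apparent prevalence is 0.10 × 0.80 + 0.90 × 0.02 = 0.098. Then (0.098 − 0.02) / 0.78 = 0.10, or 33.8 of 338, which is the true value.

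**The discordant case.** For a charted COVID-19 diagnosis with a negative antibody test, XX.B counts the person as diagnosed, while XX.D says the person was not infected. No passage says which source prevails.

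**The case against.** The case on the other side has real force.

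- A reader might infer that the infected count will be wrong. The documents do not support that. They give no assay performance or prevalence, and the two kinds of error can offset: in two of the three scenarios the net error is under one person. What remains is that a correct total can still hold the wrong individuals, which matters for symptoms and asymptomatic share.
- A reader might infer that every infection result rests on the antibody test. It does not. Diagnoses and symptoms come from records and interviews, the antibody item in XX.B is correctly worded as a count of people with antibodies, and deaths come from chart review. XX.E also says the survey has value without the blood draw.
- A reader might infer that the sub-study plans to reclassify charted cases as uninfected. The statement sits among notes under Relevance, not in Methods, and XX.B would still count that person as diagnosed. The conflict follows from a literal reading plus a missing rule, not from an announced procedure.
- Choosing the assay later, with specialist advice, is not an error. Its performance figures can be applied only after that choice.
- Waning antibodies and vaccination are tempting arguments, but Section XX raises neither, and the point does not need them.

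**Conclusion.** The point holds as a wrong stated rule in the sub-study. XX.D treats both antibody results as proof, which the documents do not justify, and taken literally this contradicts diagnoses collected elsewhere in the same section. The consequence is exposure to individual misclassification, with no correction and no rule for discordant results.

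The documents fix neither the direction nor the size of the error in the infected count. The three scenarios give about 2–7 missed, 2–6 false positives, a net error of about −1 to +3, and 5–32% of positives false. They rest wholly on assumed prevalence, sensitivity and specificity, and on all 338 being tested; other pairings within the same ranges move the net error to between about −5 and +6.

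The text should be changed for the sub-study. It would be wrong to infer any effect on the trial itself: Section XX states that its questions are unrelated to the original design and outcomes, and no endpoint, sample size or error rate is touched.

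**What to change.** 1. In XX.D, replace the claims of knowledge with *serologic evidence of past infection* for a positive result and *no serologic evidence of past infection* for a negative one.
2. In XX.C, define past infection as a documented diagnosis or positive virus test, or a positive antibody test, so that a negative antibody result does not override a documented diagnosis. Report how many participants are discordant.
3. Report seroprevalence separately, among those actually tested, with a 95% confidence interval and a Rogan-Gladen adjustment that uses the chosen assay's sensitivity and specificity. Apply the adjustment to seroprevalence only. It does not correct the composite in item 2, which keeps any false-positive antibody results, and the report should say so.
4. Add test error to XX.E.

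The cost is wording and one simple calculation once the assay is known, with no new samples or visits. The downside is a less definite statement about who was infected.
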